### EXPLORATORY EFFICACY PARAMETERS:

- Changes from Baseline in carotid normalized wall index assessed by 3T-MRI from baseline to week 24 and week 48.
- Changes from baseline to week 24 and week 48 of potential markers on vessel wall biology including and not restricted to laboratory variables such as absolute and relative change in high sensitivity C-reactive protein (hs-CRP), MMP-9 and other selected inflammatory markers (TNF $\alpha$ , IL-6), soluble VCAM-1, PON-1 and sMCP1, plaque characterization indexes using 3T-MRI.
- Cholesterol efflux capacity after CER-001 administration.
- Changes from baseline of ApoA-1 level.
- Changes from baseline in total cholesterol, unesterified cholesterol, esterified cholesterol, triglycerides, apolipoprotein B, other apolipoprotein and lipoprotein profiles for total and unesterified cholesterol by HPLC.

### OTHER EFFICACY PARAMETERS:

- Change from baseline after 72 week treatment with CER-001 on carotid Mean Vessel Wall Area (MVWA) using 3T-MRI when administered to patients with genetically defined FPHA
- Change from baseline after 72 week treatment with CER-001 on femoral artery using 3T-MRI when administered to patients with genetically defined FPHA

### SELECTION OF STUDY PATIENTS

Patients with ApoA-1  $\leq$  110mg/dL and HDL  $\leq$  35 mg/dL, with suspected homozygous or heterozygous mutation in the *ABCA1*, and/or *ApoA-1* genes confirmed by genetic testing, and background of symptomatic or asymptomatic cardiovascular disease, will be eligible for this study..

Patients who fulfill all inclusion/exclusion criteria, including confirmation of a genetic defect, may be enrolled in the study.

### INCLUSION CRITERIA

Eligible patients must meet the following criteria before they are enrolled in the study:

1. Male and female patients, aged 18 and above.
2. Female patients who are not either surgically sterile (e.g., tubal ligation or removal of ovaries or uterus) or post-menopausal (no spontaneous menstrual periods for at least one year) must agree to use one of the following forms of contraception from screening until 90 days after the completion of the study medication: (1) systemic hormonal treatment (2) an IUD which was implanted at least 2 months prior to screening or (3) "double-barrier" contraception (condom, diaphragm and spermicide are each considered a barrier), or (4) agree to remain sexually abstinent during the entire study period (when contraception is not acceptable for cultural or religious beliefs)

3. Sign written informed consent after the scope and nature of the investigation have been explained to them before screening evaluations and willing to comply with the study restrictions
4. Are fluent in the language of the investigator, study staff (including raters), and the informed consent
5. Diagnosis of genetically confirmed HDL-c deficiency due to defects in genes coding for e.g. ABCA1 and/or ApoA-1
6. IF the subject is on lipid-lowering therapy or NEEDS to be treated with lipid-lowering therapy then the subject must be on a stable dose at least 6 weeks prior to the baseline procedures.
7. Background symptomatic or asymptomatic cardiovascular disease should be present as such:
  - For symptomatic cardiovascular disease: i) history of cardio or cerebrovascular events, ii) diagnosed coronary artery disease (CAD), iii) diagnosed carotid or peripheral stenosis, iv) previous myocardial revascularisation - percutaneous coronary intervention (PCI), or coronary artery bypass graft (CABG).
  - For asymptomatic cardiovascular disease: patients with subclinical atherosclerosis diagnosed using imaging method such as i)vDoppler ultrasound, ii)vB-mode ultrasonography – measurement of carotid intima media thickness, iii)vintravascular ultrasonography, iv) Computed Tomography, v) Magnetic Resonance Imaging
8. ApoA-1  $\leq$  110 mg/dL
9. HDL-cholesterol  $\leq$  35 mg/dL or 0.9 mmol/L

## EXCLUSION CRITERIA

### **Patients meeting any one of the following criteria are not eligible for the study:**

1. Patient with LCAT mutation will be excluded
2. Patient who experienced a cardiovascular event within 6 months prior to the start of screening
3. Patient who experienced stroke or other cerebrovascular event within 1 year prior to the onset of screening
4. Patients with triglycerides level above 500 mg/dL
5. The patient has evidence of clinically significant, uncontrolled or unstable cardiovascular, renal, hepatic (incl. AST or ALT at or above 3x ULN, or bilirubin at or above 2x ULN), gastrointestinal, hematologic, immunological, neurological, endocrine, metabolic or pulmonary disease (as determined by medical history, clinical laboratory or ECG results, or physical examination) or any other medical disorder that would increase the risk associated with taking study medication or would confound the interpretation of study results.
6. Patients with a body mass index (BMI)  $<$  17 kg/m^2 or  $>$  40 kg/m^2
7. Patients with severe anemia defined as hemoglobin level below or equal to 10 g/dL

8. Any clinically significant abnormal laboratory data, vital signs, physical examination at screening or baseline, which in the opinion of the investigator, would interfere with safety assessments
9. Clinically significant ECG abnormality at screening, including sinus bradycardia (resting heart rate < 50 beats per minute), 2nd or 3rd degree atrioventricular block, prolonged QTc (QTcF  $\geq$  450 ms in males and  $\geq$  470 ms in females) history of congenital long QT syndromes, or risk of Torsades de Pointes because of family history of sudden death, etc.
10. Positive result on the serum pregnancy test or are breast feeding at screening, or intend to become pregnant during the course of the trial
11. Male intending to father a child during the study
12. Likely to be unreliable as a study participant based on the Investigator's (or designee's) knowledge of the patient (e.g., alcohol or other drug abuse, inability or unwillingness to adhere to the protocol, or psychosis)
13. Symptomatic (NYHA Class II or greater) congestive heart failure requiring and persisting despite appropriate medical treatment
14. Uncontrolled blood pressure: systolic blood pressure  $\geq$ 160 mmHg and/or diastolic blood pressure  $\geq$ 100 mmHg at screening or any other pre-randomization visit
15. Uncontrolled diabetes mellitus defined as HbA1c  $>$ 10%
16. Unexplained creatine phosphokinase level  $>$  3 times the ULN
17. History of malignancy during the 3 years prior to screening, with the exception of basal cell carcinoma of the skin
18. Current alcohol or drug abuse or history thereof within 5 years prior to screening
19. Contraindication to MRI scanning such as imbedded metal (e.g., shrapnel), implanted metal objects (e.g., pacemaker), claustrophobia
20. Participated in any investigational study or taken an investigational drug within 30 days (or 5 times the half-life of the investigational drug, whatever is longer)
21. Ever received CER-001 within 6 months before the start of screening
22. Medically non-compliant in the management of their disease in the investigator's opinion

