**Figure 1. Schematic study design.**

### 6.1.1 Study periods

The study duration can be up to 68 to 92 weeks in total:

- Screening period: up to 16 weeks (+/- 7 days)
- Treatment period: the overall treatment period is 48 weeks (+/- 7 days) including an induction treatment phase of 8 weeks, followed by a 16 week maintenance treatment phase and a 24 week extension treatment phase.
- Safety follow-up period: 4 weeks (+/- 7 days) after the end of treatment OR
- Safety extension follow-up: 24 weeks (+/- 7 days) AND Safety follow-up period: 4 weeks (+/- 7 days) after the end of treatment

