## 8.1 Screening Examination and Eligibility Screening Form

All patients must provide written informed consent before any study specific assessments or procedures are performed. An Eligibility Screening Form (ESF) documenting the investigator's assessment of each screened patient with regard to the protocol's inclusion and exclusion criteria is to be completed by the investigator. A screen failure log must be maintained by the investigator.

### Visit 1

This is the first visit of the study. This visit will be performed after obtaining written informed consent. The investigator will advise the patient on heart healthy diet and life style.

Screening assessments include:

- Informed Consent
- Inclusion/exclusion criteria
- Demographic information
- Smoking status
- Measurement of height and body weight
- Medical history/surgical history and concomitant diseases
- Previous and concomitant treatments
- Physical exam (See Section 8.8.1)
- Vital Signs (See Section 8.8.2)
- Blood Pressure and Heart Rate
- ECG (See Section 8.8.3)
- Serum biochemistry (See Section 8.8.4)
- Hematology and coagulation (See Section 8.8.4)
- Urinalysis (See Section 8.8.4)
- Fasting lipid profile (See Section 8.9), including Apolipoprotein profile.
- Anti-ApoA-1 antibody (See Section 8.8.5)
- Markers of inflammation, oxidation, lipid metabolism and CV risk (See Section 8.10)
- Serum pregnancy test in female patients (See Section 11.8)
- FSH (only for women whose last menstrual period was between 6 and 12 months before screening)
- Fasting blood glucose and HbA1c
- Creatinine and/or BUN testing to determine GFR

Patient must have fasted (ie not to take any food or liquids other than water) for 8 hours prior to blood sampling.

A DNA sample will be taken ONLY for determination of the presence of HDL gene mutations specifically for ABCA1 and/or ApoA-1 mutation(s) to ensure that the patient was to satisfy all inclusion and exclusion. Genotyping will be performed at the Robarts Research Institute, London, Canada.

**Following visit 1, if a patient is eligible according to all of the inclusion and exclusion criteria, he/she will be instructed to come in fasted for the randomization visit 2.**

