## **8.2 Procedures for Enrollment of Eligible Patients and Assessment at Visit 2**

Once a patient has fulfilled all inclusion and exclusion criteria, he/she will be randomized at visit 2 to receive CER-001 or placebo using an interactive voice response system (IVRS/IWRS). The investigator/designee will contact the IVRS/IWRS to randomize a patient for this study and will be given a patient number and a randomization number. The investigator or designee will use the eCRF with the assigned patient number and the IVRS/IWRS will automatically download the treatment allocation and randomization number as well as the patient number for the patient into the eCRF.

The following assessments will be performed at visit 2 (V2):

- Physical exam (See *Section 8.8.1*)
- Blood Pressure and Heart Rate
- Measurement of weight and vital signs (See *Section 8.8.2*)
- ECG (See *Section 8.8.3*)
- Blood samples for
  - Hematology and coagulation (See *Section 8.8.4*)
  - Serum chemistry (See *Section 8.8.4*)
  - Fasting lipid profile (See *Section 8.9*)
  - Markers of inflammation, oxidation, lipid metabolism and CV risk (See *Appendix A*)
  - Fasting blood glucose and HBA1c
  - Protein biomarker assessment
- Urinalysis (See *Section 8.8.4*)
- Pregnancy test
- Previous and concomitant medication
- Adverse events
- Creatinine and/or BUN testing to determine GFR

Patient must have fasted (ie not to take any food or liquids other than water) for 8 hours prior to blood sampling.

The first 3T-MRI and the first FDG-PET/CT scan assessing the carotid and femoral artery will be optimally performed at this visit prior to the first infusion.

After all assessments have been performed the patient will be administered the first infusion as described in Section 9.6.

He/she will stay for an additional hour after the infusion to ensure completion of the overall examination. A blood sample will be drawn two hours after initiation of the infusion to assess the pharmacokinetics of the study drug.

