### **8.8.4 Clinical Laboratory Tests**

Laboratory tests should be measured at the screening visit, randomization, at week 4, week 8 and every 8 weeks thereafter until the end of treatment. Additionally, laboratory tests will be done at the follow-up visit. Any blood sample collected according to the Schedule of Assessments (Appendix A) may be analyzed for any of the tests outlined in the protocol. This may also include, but is not limited to, investigation of unexpected results and incurred sample reanalysis.

Clinical laboratory safety testing during the screening and treatment periods will be performed by a central laboratory. Collection kits, shipment instructions, and a detailed clinical laboratory manual will be provided to the study sites. Investigators are required to review the labs upon receipt and make a determination of clinical significance for labs outside of the normal range. All laboratory reports must be reviewed, signed and dated by a medically trained investigator. Clinical laboratory safety testing will consist of the following panels of laboratory tests. The details of which tests are performed at each visit can be found in Appendix A.

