## APPENDIX A: Schedule of Assessments in double-blind treatment phase

	Screening V1	Randomization Baseline V2 W0	Period 1 Induction Infusion every week				Period 2 Maintenance Infusion every two weeks				Period 3 Extension				Period 3 Extension			Final safety V31 W52
			V3 to V5 W1 to W3	V6 W4	V7 to V9 W5 to W7	V10 W8	V11 to V13 W10 to W14	V14 W16	V15 to V17 W18 to W22	V18 W24	V19 to V21 W26 to W30	V22 W32	V23 to V25 W34 to W38	V26 W40	V27 to V29 W42 to W46	V30 W48		
Informed consent	X																	
Selection criteria	X																	
Demography	X																	
Medical history (smoking status)	X																	
Counseling on heart healthy diet and lifestyle	X																	
Vital signs	X	X		X		X		X		X		X		X		X	X	
Blood pressure & heart rate assessment	X	X		X*		X*		X*		X*		X*		X*		X*	X	
*BP and HR should be measured pre-infusion and post-infusion																		
Height	X																	
Weigh	X	X		X		X		X		X		X		X		X	X	
Physical exam	X	X		X		X		X		X		X		X		X	X	
12-lead ECG	X	X		X		X		X		X		X		X		X	X	
Adverse events 		X	X	X	X	X	X	X	X	X	X	X	X	X	X	X	X	
Previous and concomitant medications	X	X	X	X	X	X	X	X	X	X	X	X	X	X	X	X	X	
FSH 	X																	
Serum Pregnancy Test	X																	
Urinary Pregnancy Test			X		X		X		X		X		X		X		X	
Hematology/coagulation 	X	X		X		X		X		X		X		X		X	X	
Serum chemistry 	X	X		X		X		X		X		X		X		X	X	
Urinalysis 	X	X		X		X		X		X		X		X		X	X	
Markers of inflammation, oxidation and CV risk 	X	X		X		X				X							X	
Anti-ApoA-1 antibody	X					X				X							X	
Fasting plasma glucose 	X	X		X		X		X		X		X		X		X	X	
HbA1c	X	X																
Biomarkers sample		X									X							
Lipid & Lipoprotein profile  (from fastingsamples)	X	X				X					X						X	
Cholesterol Eflux 	X	X				X				X							X	
Genotyping 	X																	
Study drug infusion 			X	X	X	X	X	X	X	X	X	X	X	X	X	X	X	
Pharmacokinetics  (2 hours after starting the infusion)			X								X							
3T MRI (MVWA)			X			X					X						X	
18FDG-PET/CT (if site equipped to do it)			X								X							

1. AEs and SAEs (related or not related) to be recorded at each visit until the final study evaluation. After the end of the study, only the SAEs likely to be related to the study medication or study procedures must be notified.

2. FSH in women whose last menstrual period was between 6 and 12 months before screening

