6.2 Protocol deviations

A list of protocol deviations has been written by ICTA PM and sent to the sponsor for approval. The list contains possible protocol deviations (according to inclusion/exclusion criteria, disallowed treatments, minimum treatment exposure, and calendar of visits...), and significant deviations which require immediate information to the Sponsor. This list may be updated in the course of the data management process, and will be finalized during the data review meetings before database lock and unblinding.

TANGO_DeviationsLi

During the data review, the impact of each deviation (minor/major) on the primary endpoint will be discussed and thus, the list of patients to be excluded from the PP population will be defined.

Number and percentage of patients with at least one deviation, at least one major deviation, at least one deviation by type (Entry criteria / Study procedures / Investigational medicinal product) will be described. Each deviation will also be summarized by the number and percentage of patients who experienced it.

6.3 Disposition of patients

The following data will be described:

- Number of screened patients [a]
- Number of screening failures and reasons for screening failures
- Number of randomized patients grouped by treatment
- Number of patients for whom the blind was broken
- Number of patients with ABCA-1, ApoA-1 or both mutations
- Number of patients who did not receive any medication and reason for non-treatment
- Number of patients who received double-blind medication
- Treatment actually received (CER-001/Placebo)
- Number of patients who completed the study
- Number of premature discontinuations of the study treatment and reason for premature discontinuation (at each visit, and overall)
- Number of premature withdrawals and reason for premature withdrawal (at each visit, and overall)
- Number of patients who completed the induction period grouped by treatment (visit at W8 performed)
- Number of patients who completed the maintenance period grouped by treatment (visit at W24 performed)
- Number of patients who completed the extension period grouped by treatment (visit at W48 performed)
- Patient's follow-up duration
- Inclusion date of the first patient (FPFV: First Patient First Visit), date of first visit of the last patient (LPFV) and last visit date of the last patient (LPLV: Last Patient Last Visit)
- Number of patients in each analysis set and reasons for exclusion from the analysis sets

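### The baseline laboratory part of exclusion criterion 8 cannot be relied on to gate entry, and SAP 6.1 read literally would drop a patient whose breach is found after dosing

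*Protocol*

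**What the plan says.** Criterion 8 stands in the same terms in the synopsis and in protocol 7.3. It excludes "Any clinically significant abnormal laboratory data, vital signs, physical examination at screening or baseline, which in the opinion of the investigator", provided the abnormality could compromise the safety evaluation. Criterion 9, on ECG abnormalities, refers to screening alone, so the mention of baseline in criterion 8 adds a condition.

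Appendix A labels the baseline column "Randomization Baseline V2 W0". Protocol 8.2 lists haematology, coagulation, serum chemistry and urinalysis among the visit 2 assessments, then states: "After all assessments have been performed the patient will be administered the first infusion as described in Section 9.6". Section 10.1 confirms that the first dose is given at that visit. Section 8.8.4 states: "Clinical laboratory safety testing during the screening and treatment periods will be performed by a central laboratory". It adds that sites receive shipment instructions and that investigators judge clinical significance when the results reach them.

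On when eligibility is settled, 8.1 calls a patient to visit 2 "if a patient is eligible according to all of the inclusion and exclusion criteria", 8.2 says "Once a patient has fulfilled all inclusion and exclusion criteria, he/she will be randomized at visit 2", and Appendix A marks selection criteria at visit 1 only.

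SAP 6.1 opens by making fulfilment of all entry criteria a condition for belonging to any of its three populations. It then defines the safety population as all randomised patients who received at least one dose. On deviations, SAP 6.2 says "The list contains possible protocol deviations (according to inclusion/exclusion criteria, disallowed treatments, minimum treatment exposure, and calendar of visits". Each deviation is graded minor or major for its impact on the primary endpoint, before database lock and unblinding.

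**The concern.** The criterion names a result that the protocol does not require anyone to have when it must be applied. If a visit 2 value is judged clinically significant only after the infusion, the patient becomes an eligibility breach on an opinion formed after randomisation and dosing.

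The stake is who is analysed. The criterion is aimed at abnormalities that would interfere with safety assessments. Removing such patients from the safety population would take out treated patients of particular safety interest, and removing them from the mITT population would be a post-randomisation exclusion in a trial of 30. Protocol 12.5 points the other way: it includes mITT patients whatever their protocol adherence and bases safety on everyone dosed. The SAP says that it supersedes the protocol, and its section 10 does not list this change.

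**Working it through.** **Order of events**

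1. Visit 1: screening laboratory tests, vital signs and physical examination. Eligibility on all criteria is decided after this visit (8.1; Appendix A).
2. Visit 2: randomisation, conditional on all criteria being met (8.2).
3. Visit 2: blood and urine collected, vital signs and examination done (8.2).
4. Visit 2: first infusion once assessments have been carried out (8.2, 10.1). The trigger is that they were done, not that results were received.
5. Unstated time: central laboratory result received and judged (8.8.4).

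No section gives a local or rapid pre-dose test, a turnaround time, a hold on the infusion until results arrive, or a rule for a breach found afterwards.

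**Which parts of criterion 8 can be applied in time**

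| Element | Visit 1 | Visit 2 |
|---|---|---|
| Laboratory data | yes | not assured |
| Vital signs | yes | yes |
| Physical examination | yes | yes |

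One cell of six is affected.

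**Age of the laboratory results in hand at first dose**

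Protocol 6.1.1 gives "Screening period: up to 16 weeks (+/- 7 days"). Maximum: 16 × 7 + 7 = 119 days. The documents give no typical interval.

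**Power, as context only**

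Inputs from protocol 12.4: difference 6.7%, SD 4.5%, 16 and 8 completers, two-sided 0.05. Two-sample t-test: noncentrality = 6.7 / (4.5 × √(1/16 + 1/8)) = 3.438, 22 degrees of freedom, critical value 2.074, power 90.7%. This reproduces the stated 90%. The allowance for discontinuation also reproduces: 24 / (1 − 0.20) = 30.

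The documents give no breach rate, so these are assumptions. If 2%, 5% or 10% of 30 patients had a disqualifying visit 2 result:

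- expected number: 0.6, 1.5 or 3.0;
- chance of at least one, 1 − (1 − rate)^30: 45%, 79% or 96%.

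Power by the same formula if patients were removed:

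| Starting point | None | One active | One placebo | Two placebo |
|---|---|---|---|---|
| 16:8 (after the full 20% loss) | 90.7% | 90.0% | 87.9% | 84.1% |
| 20:10 (all 30 retained) | 96.0% | 95.7% | 94.7% | 92.9% |

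The answer ranges from no loss to several points, depending on assumptions that the plan does not supply. The point does not rest on it.

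**The case against.** The best defence is that screening decides entry in practice. Section 8.1 and Appendix A settle selection at visit 1, screening laboratory results do gate entry, and vital signs and examination can be judged at both visits. A reader might infer that criterion 8 as a whole can only be found broken after dosing. The documents do not support that: only the visit 2 laboratory clause is exposed. Nor do they say that results arrive days later. Handling details sit in a laboratory manual that is not part of these documents, and a same-day result is not ruled out, though nothing requires one.

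The safety argument also has limits. Protocol 11.7 reports no significant laboratory abnormalities associated with the drug in humans, and 11.6 reports no excess over placebo for liver enzymes or red-cell indices. Section 11.7 ties later dosing to the most recent transaminase values, so a late visit 2 liver result would still count for subsequent infusions.

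On the per-protocol set, SAP 6.2 does not exclude automatically. It grades each deviation for impact on the primary endpoint before unblinding, and a blood value has no evident bearing on MRI wall area. That largely answers a worry about PP exclusions, though not about the other two populations.

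It is fair to add that the opening condition in SAP 6.1 would catch any entry breach, not just this one. That makes SAP 6.1 the more important place to amend. The conflict between criterion 8 and section 8.2 remains.

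**Conclusion.** The point holds, limited to the baseline laboratory clause of criterion 8. As written, that clause cannot be relied on to gate entry: the sample is drawn at the randomisation and infusion visit, tested centrally, and not required to be read first, while 8.2 says every criterion has already been met. That results come after dosing is a reasonable inference from shipment and same-visit infusion, not a documented fact.

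The consequence depends on reading SAP 6.1 literally. Its opening condition would then remove a randomised, dosed patient from the safety, mITT and PP populations on a judgement made after dosing, against its own definition of the safety population.

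A reader might infer a quantified loss of power. The documents do not support one: no breach rate is given, and the larger losses shown assume that only placebo patients go, from 24 completers. Likewise, 119 days is the longest that screening results could have aged, not what is expected. This should be corrected because the rule affects who is analysed and the correction is cheap.

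**What to change.** - **Protocol (synopsis and 7.3, criterion 8; 8.1; 8.2; 8.8.4; Appendix A):** reconcile these so that they name the laboratory results that decide eligibility and say that those results must be available before randomisation. Which results these are is for the sponsor to decide.
- **SAP 6.1:** remove the all-criteria condition from the safety and mITT populations, so that a breach first known after randomisation never removes a patient from either. This also restores agreement with protocol 12.5.
- **SAP 6.2:** record as a deviation any visit 2 result that still breaches the criterion as finally worded, and grade it blinded, for the PP population only. Declaring such results not to be deviations while criterion 8 still mentions baseline would create a new conflict between protocol and SAP.

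The cost is a few sentences in each document. No analysis, sample size or endpoint changes. There is an operational cost only if the sponsor decides that a baseline result must be in hand before randomisation.
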